**Table 12: Comparison between outcome measures before and after treatment in group B (NAC):**

	Mean	SD	t*	P value
VAS score for dysmenorrhea before	7.30	1.78	6.49	0.00
VAS score for dysmenorrhea after	3.70	1.69		
Hemoglobin level before	11.39	1.46	1.40	0.18
Hemoglobin level after	11.63	1.51		
	Median	IQR	Z**	P value
Leiomyoma volume (cm3) before	9.00	4.09-14.32	3.46	0.001
Leiomyoma volume (cm3) after	13.13	7.74-24.16		
HMB assessment (PBAC) before	50.00	15.00-90.00	1.78	0.08
HMB assessment (PBAC) after	25.00	15.00-70.00		

\*Paired-samples t test    \*\* Wilcoxon Signed Ranks Test

Similar to Group A, Group B also shows significant improvements in VAS scores and increase in leiomyoma volume, though the changes in hemoglobin levels and HMB assessments are less pronounced.

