**Table 10: Comparison between two groups regarding hemoglobin level before and after treatment:**

	Group A (Dienogest) (N=20)			Group B (NAC) (N=20)			t*	P value
	Range	Mean	SD	Range	Mean	SD		
Hemoglobin level before	7.60-12.80	10.54	1.65	9.30-13.60	11.39	1.46	1.73	0.09
Hemoglobin level after	8.20-13.20	10.99	1.41	7.90-13.80	11.63	1.51	1.39	0.17

\*Student t test

While hemoglobin levels increase slightly in both groups after treatment, the differences between the groups are not statistically significant ( $p > 0.05$ ).

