**Comparison of outcome measures before and after treatment:**

**Table 11: Comparison between outcome measures before and after treatment in group A (Dienogest):**

	Mean	SD	t*	P value
VAS score for dysmenorrhea before	7.10	2.88	7.74	0.00
VAS score for dysmenorrhea after	1.35	2.35		
Hemoglobin level before	10.54	1.65	2.78	0.01
Hemoglobin level after	10.99	1.41		
	Median	IQR	Z**	P value
Leiomyoma volume (cm3) before	15.53	4.31-25.01	2.78	0.01
Leiomyoma volume (cm3) after	19.54	8.25-32.61		
HMB assessment (PBAC) before	70.00	15.00-110.00	2.88	0.004
HMB assessment (PBAC) after	0.00	0.00-8.50		

\*Paired-samples t test    \*\* Wilcoxon Signed Ranks Test

Significant improvements are observed in VAS scores, HMB assessment, and hemoglobin levels after treatment, suggesting that Dienogest is effective. But leiomyoma volume is significantly increased after treatment.

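### The SAP text under Table 12 contrasts the arms on hemoglobin using separate within-arm tests; no table tests the difference in change, and the printed figures show no statistically significant one

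*SAP*

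**What the plan says.** The protocol (Outcomes) lists hemoglobin as one of the measures of heavy menstrual bleeding, a secondary outcome. The SAP reports it in three places.

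- Table 10 compares the arms on hemoglobin level at each time point (P = 0.09 before, P = 0.17 after) and concludes that "the differences between the groups are not statistically significant".
- Table 11 tests group A (dienogest) against its own baseline: "Hemoglobin level before 10.54 1.65 2.78 0.01" and "Hemoglobin level after 10.99 1.41", the last two figures of the first row being the paired t and its P-value.
- Table 12 does the same for group B (NAC): "Hemoglobin level before 11.39 1.46 1.40 0.18" and "Hemoglobin level after 11.63 1.51".

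The sentence under Table 12 begins by likening group B to group A on dysmenorrhea and leiomyoma volume, then qualifies this: "though the changes in hemoglobin levels and HMB assessments are less pronounced". No table compares the two arms on the change in hemoglobin.

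**The concern.** Because the sentence opens with group A as its reference, its last clause reads as a comparison between arms. For hemoglobin, the only results that separate the arms in this part of the SAP are the two paired tests, one below 0.05 and one above. Each asks whether one arm moved from its own baseline. Neither asks whether the arms moved by different amounts, which is the question a randomized comparison is designed to answer. With 20 women per arm, paired tests can fall on opposite sides of 0.05 when the between-arm difference is well within chance.

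Two features make the clause easy to over-read. It joins hemoglobin to the bleeding score, which does have a between-arm test after treatment (Table 9, Z = 4.10), so a reader may assume the same support for hemoglobin. It also leaves out that the dienogest arm started lower, which by itself favors a larger rise in that arm.

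**Working it through.** **Inputs.** Hemoglobin means and SDs: Tables 10, 11 and 12. Paired t values: 2.78 (Table 11) and 1.40 (Table 12), both from a "Paired-samples t test". Number per arm: 20 (Table 10). The tables print no hemoglobin unit, so none is given here.

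**1. Reproduce the SAP's figures.**
- Paired tests on 19 df: t = 2.78 gives P = 0.012 (printed 0.01); t = 1.40 gives P = 0.178 (printed 0.18).
- Table 10, before: 0.85 / sqrt((1.65² + 1.46²)/20) = 0.85/0.493 = 1.73, P = 0.093 (printed 0.09).
- Table 10, after: 0.64 / sqrt((1.41² + 1.51²)/20) = 0.64/0.462 = 1.39, P = 0.174 (printed 0.17).

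All four agree.

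**2. Change within each arm.** SE of mean change = mean change / paired t.
- A: 10.99 - 10.54 = 0.45; SE = 0.45/2.78 = 0.162; 95% CI 0.45 ± 2.093 × 0.162 = 0.11 to 0.79.
- B: 11.63 - 11.39 = 0.24; SE = 0.24/1.40 = 0.171; 95% CI 0.24 ± 2.093 × 0.171 = -0.12 to 0.60.

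**3. Direct comparison of the changes.**
- Difference A - B = 0.45 - 0.24 = 0.21.
- SE = sqrt(0.162² + 0.171²) = 0.236.
- t = 0.21/0.236 = 0.89 on 38 df, P = 0.38 (Welch, 37.9 df: the same).
- 95% CI = 0.21 ± 2.024 × 0.236 = -0.27 to 0.69.
- Varying the printed means and t values within their rounding moves P only between 0.33 and 0.43.

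**4. Adjustment for baseline (ANCOVA rebuilt from summaries).**
- SD of change = SE × sqrt(20): A 0.724, B 0.767.
- Implied before-after correlation = (SD_before² + SD_after² - SD_change²) / (2 × SD_before × SD_after): A 0.90, B 0.87.
- Pooled within-arm sums: Sxx = 19(1.65² + 1.46²) = 92.2; Sxy = 19(0.900 × 1.65 × 1.41 + 0.867 × 1.46 × 1.51) = 76.1; Syy = 19(1.41² + 1.51²) = 81.1.
- Slope = 76.1/92.2 = 0.825.
- Adjusted difference = (10.99 - 11.63) - 0.825 × (10.54 - 11.39) = -0.64 + 0.70 = 0.06.
- Residual mean square = (81.1 - 76.1²/92.2)/37 = 0.495; SE = sqrt(0.495 × (2/20 + 0.85²/92.2)) = 0.231.
- t = 0.27 on 37 df, P about 0.79; 95% CI = 0.06 ± 2.026 × 0.231 = -0.41 to 0.53.

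**The case against.** The best defense is that the clause is plain description, and true: 0.24 is smaller than 0.45. It cites no P-value and claims no significant difference. It could even be read within group B, where dysmenorrhea and volume changed significantly while hemoglobin (P = 0.18) and the bleeding score (P = 0.08) did not. Table 10 already tells the reader that hemoglobin levels do not differ significantly between arms.

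Much of this stands, and it limits the point. A reader might infer that the SAP claims a proven hemoglobin advantage for dienogest. It does not: its one explicit between-arm statement on hemoglobin denies a significant difference. What remains is that the sentence takes group A as its reference, sits among significance tests, and gives no estimate or interval for the contrast. Table 10 does not fill the gap, since it compares levels at each time point and not changes.

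It can also be objected that the figures above are back-calculated from rounded summaries. That is a good reason not to print them in the SAP, and to run the analysis on patient data.

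**Conclusion.** The point holds as a minor one, for hemoglobin only. The contrast under Table 12 has no between-arm test behind it. The unadjusted difference in change is 0.21 (95% CI -0.27 to 0.69, P about 0.38). Allowing for the baseline gap leaves about 0.06 (95% CI -0.41 to 0.53, P about 0.79), so most of the apparent difference goes with the lower dienogest baseline.

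Two stronger readings should be resisted. First, a reader might infer that the arms have been shown to be alike. They have not: the upper limit of 0.69 exceeds the mean change seen in either arm. Second, a reader might infer that the bleeding-score half of the clause fails as well. It does not, because Table 9 compares the arms directly after treatment.

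The figures assume that all 20 women per arm contribute to the paired tests. The adjusted figure also assumes a common slope in the two arms, and is approximate because it uses rounded SDs and implied correlations. The primary outcome, the sample size and the tabulated hemoglobin results are unaffected.

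**What to change.** 1. Remove hemoglobin from the clause under Table 12. In its place, report an ANCOVA of post-treatment hemoglobin on arm with baseline hemoglobin as covariate, run on the patient data, giving the adjusted difference and its 95% CI. State the unit.
2. Label Tables 11 and 12 as descriptive within-arm results from which no between-arm statement is drawn.
3. Rest the bleeding-score statement on Table 9's post-treatment comparison, which tests levels and not changes. Reconcile two things first: the baseline row, where Z = 0.9 is printed with P = 0.86 (a Z of 0.9 corresponds to a two-sided P of about 0.37), and the group A post-treatment upper quartile, which is 9.00 in Table 9 and 8.50 in Table 11.

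The cost is one model on data already collected and some rewording. One descriptive statement favorable to dienogest is withdrawn.
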